7.9.2 Pharmacodynamic Analysis

Not applicable.

7.10 Other Outcomes

Daily meals during confinement in each period will be reported in the data listing.

7.11 Safety Analysis

Safety analyses include adverse events (AEs), clinical laboratory parameters, vital sign parameters, and 12-lead electrocardiogram (ECG) results.

All summaries of safety data are based on subjects in the Safety Analysis Set.

7.11.1 Adverse Events

A treatment -emergent adverse event (TEAE) will be defined as an AE or serious adverse event (SAE) that started or worsened after first study drug administration and within 30 days of last dose of study drug (onset date – date of last dose + 1 \leq 30). A TEAE will be attributed to a regimen if the TEAE occurs after administration of the study drug in a period and up to just prior to study drug administration in the next period. A TEAE that occurs after administration of the study drug dose is attributed to the regimen received in the last period. All AE verbatim terms will be coded by system organ class (SOC) and preferred term using (PT) the MedDRA coding system.

TEAEs will be summarized by regimen and overall. The tables will include the number and percentage (N [%]) of subjects reporting any event for that term. The following TEAE tables will be summarized.

- Overview of TEAEs.
- TEAEs by SOC and PT at subject and event level.
- Subject Mappings for TEAEs.
- TEAEs by PT.

- Most Frequent TEAEs by PT term
- Most Frequent Non-Serious TEAEs by PT term at subject and event level
- Relationship of TEAEs to Study Drug by SOC and PT.
- Drug-Related TEAEs by SOC and PT.
- Severity of TEAEs by SOC and PT.
- Severity of Drug-Related TEAEs by SOC and PT.

In addition, pretreatment events (PTEs) will be summarized overall by SOC and PT.

For each regimen and overall, subjects reporting more than one occurrence for a term (SOC or PT) being summarized will be counted only once using the most extreme incident (most severe for the severity tables and related for the relationship to study drug tables).

Most frequent TEAEs are those events occurred in at least \geq 5% (before any rounding) of subjects in a regimen.

Data listings will be provided for all TEAEs, PTEs, TEAEs that led to study discontinuation, TEAEs that led to abnormal liver functions, SAEs, AEs that resulted in death, and AEs occurring more than 30 days after the last dose of study medication.

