9.2 Monitoring Subject Treatment Compliance

Study medication will be administered while subjects are under observation in the clinical research unit. Following administration of the study drug, appropriate mouth and/or hand checks will be performed to ensure that the dose is swallowed and noted in the source document. The date and time of each dose will be recorded in the source documents and on the eCRFs. An inventory of the study drug supplies dispensed will be performed by the site pharmacist or authorized study designee and recorded onto the Drug Accountability Log in the subject's source document records or equivalent. The exact dose time of consecutive subjects may be staggered to facilitate logistics at the site.

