10.1.8 Start Date

The start date of the AE/PTE is the date that the first signs/symptoms were noted by the subject and/or investigator.

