10.2 Procedures

10.2.1 Collection and Reporting of AEs

10.2.1.1 PTE and AE Collection Period

Collection of PTEs will commence from the time the subject signs the informed consent to participate in the study and continue until the subject is first administered study drug (Day 1, Period 1) or until screen failure. For subjects who discontinue prior to study drug administration, PTEs are collected until the subject discontinues study participation.

Collection of AEs will commence from the time that the subject is first administered study drug (Day 1, Period 1). Routine collection of AEs will continue until check-out following the completion of all assessments on Day 1 of Period 2.

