10.2.1.2 PTE and AE Reporting

At each study visit, the investigator will assess whether any subjective AEs have occurred. A neutral question, such as "How have you been feeling since your last visit?" may be asked. Subjects may report AEs occurring at any other time during the study. Subjects experiencing a serious PTE must be monitored until the symptoms subside and any clinically relevant changes in laboratory values have returned to Baseline or there is a satisfactory explanation for the change. Non-serious PTEs, related or unrelated to the study procedure, need not to be followed-up for the purposes of the protocol.

All subjects experiencing AEs, whether considered associated with the use of the study drug or not, must be monitored until the symptoms subside and any clinically relevant changes in laboratory values have returned to Baseline or until there is a satisfactory explanation for the changes observed. All PTEs and AEs will be documented in the PTE/AE page of the eCRF, whether or not the investigator concludes that the event is related to the drug treatment. The following information will be documented for each event:

- 1. Event term.
- 2. Start and stop date.
- 3. Frequency.

- 4. Intensity.
- 5. Investigator's opinion of the causal relationship between the event and administration of study drug(s) (related or not related) (not completed for PTEs).
- 6. Investigator's opinion of the causal relationship to study procedure(s), including the details of the suspected procedure.
- 7. Action concerning study drug (not applicable for PTEs).
- 8. Outcome of event.
- 9. Seriousness.

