7.1.4 Conventions for Missing Adverse Event Dates

There will be no imputation of incomplete or missing adverse event dates.

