7.7 Study Drug Exposure and Compliance

All doses of study medication will be administered during confinement. Dosing data, including dosing time will be provided by subject and visit in the listings.

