Appendix A Schedule of Study Procedures

(a) There will be a minimum 6-day washout period between doses. Day -1 of Period 2 could be the sixth day of washout.

(b) Can be conducted up to 24 hours prior to dosing.

(c) Vital signs: oral body temperature, sitting blood pressure (after resting 5 minutes), respiratory rate, and pulse (beats per minute) at Screening. Only blood pressure and pulse will be collected on Check-in (Day -1) through Day 1 of each period, or if the subject early terminated from study. On Day 1 of each period, vital signs will be taken at predose.

(d) Height only measured at Screening.

(e) Hematology, serum chemistries, and urinalysis tests.

(f) For women where menopause is suspected.

(g) Study drug administered beginning at approximately 0800 hours.

(h) Blood samples for PK obtained predose (within 15 minutes prior to dose), and at 0.33, 0.66, 1, 1.33, 1.66, 2, 2.33, 2.66, 3, 3.5, 4, 4.5, 5, 6, 7, 8, 9, and 10 hours postdose on Day 1 of each period. The PK sample should not be collected on Early Termination if a PK collection is not scheduled.

(i) Pretreatment adverse events will be captured immediately following the signing of the informed consent at Screening until dosing on Day 1 of Period 1. The routine collection of AEs will continue after dosing through to check out on Period 2, Day 1.

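### Does the lack of an adverse event onset time make the SAP's regimen attribution rule unworkable on the Period 2 dosing day?

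*SAP*

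**What the plan says.** SAP 7.11.1 gives a TEAE to the regimen of a period if it "occurs after administration of the study drug in a period and up to just prior to study drug administration in the next period". A further sentence gives events after what appears to be the final dose to the regimen of the last period. TEAEs are tabulated by regimen and overall.

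On onset, Protocol 10.1.8 reads: "The start date of the AE/PTE is the date that the first signs/symptoms were noted by the subject and/or investigator". Protocol 10.2.1.2 lists nine items to document for each event. One is "Start and stop date"; none is a clock time, a period or a regimen.

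On dosing, Protocol 9.2 says: "The date and time of each dose will be recorded in the source documents and on the eCRFs". SAP 7.7 adds: "Dosing data, including dosing time will be provided by subject and visit in the listings".

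On conventions, SAP 7.1.4 states: "There will be no imputation of incomplete or missing adverse event dates". No rule covers an onset date that equals a dosing date.

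On the end of collection, Protocol 10.2.1.1 says: "Routine collection of AEs will continue until check-out following the completion of all assessments on Day 1 of Period 2". SAP Appendix A, note (i), agrees: "The routine collection of AEs will continue after dosing through to check out on Period 2, Day 1".

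**The concern.** The rule compares two moments, and the documents promise a clock time for only one of them. Dosing is at about 0800 and subjects leave the unit the same day, so every routinely collected event that starts after the Period 2 dose carries the Period 2 dosing date. An event that starts at 0600 that morning belongs to the Period 1 regimen under the rule, but carries the same date.

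On Period 1 Day 1 the split between pretreatment events and adverse events settles the same tie. No such label exists at the Period 2 dose.

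At stake is the by-regimen split in the TEAE tables: incidence, severity, relationship to drug, and the table of events in at least 5% of subjects. If two programmers handled the tie differently, those tables would differ.

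**Working it through.** The plan gives no figure to reproduce here, so the check is date arithmetic on its own timeline.

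**Inputs.** Dose at about 0800 on Day 1 (Protocol 8.1.3). Last PK sample at 10 h (Protocol Table 9.b), with a 10-minute window (Protocol Table 14.a). Discharge the same day (Protocol 9.3.3). At least 6 days between doses (Protocol 7.4.1). 26 subjects per sequence, 52 in all (Protocol Table 8.b).

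**Step 1: is there a tie?** 0800 + 10 h 10 min = 1810, the same calendar date. In the SAP's 30-day formula, onset date minus last dose date plus 1 equals 1, so the event is a TEAE wherever it falls on that date. The tie is real, but it affects only the regimen label. It covers the Period 2 dosing day of all 52 subjects, 26 on each regimen.

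**Step 2: what does the date resolve?** Take the ordinary default: an onset on a dosing date goes to that day's regimen.

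| Onset | Regimen under the SAP rule | Regimen by date and default | Agree? |
|---|---|---|---|
| Period 1 Day 1, recorded as an AE | Period 1 | Period 1 | yes |
| Next day to Period 2 Day -1 | Period 1 | Period 1 | yes |
| Period 2 Day 1, before the dose | Period 1 | Period 2 | no |
| Period 2 Day 1, after the dose | Period 2 | Period 2 | yes |
| Later date (SAE reported after check-out) | Period 2 | Period 2 | yes |

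One row fails: new events first noted between 0000 and about 0800 on one date per subject.

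**Step 3: how wide is that window?** Observation from the Period 1 dose to the 10 h sample in Period 2 is at least 6 × 24 + 10 = 154 h. The window is 8 h, and 8/154 = 5.2%. A longer washout or a later check-out lowers this share; a staggered dose at, say, 0900 would give 9/154 = 5.8%. This is a share of time, not of events.

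**Step 4: what does one misplaced subject do?** 1/52 = 1.9 percentage points. The 5% table needs 0.05 × 52 = 2.6, so 3 subjects (3/52 = 5.8%; 2/52 = 3.8%). With 48 subjects, 0.05 × 48 = 2.4, again 3 (6.3% against 4.2%). A term enters or leaves that table only if it sits at exactly 2 or 3 subjects.

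**Step 5: is there a rival reading?** A programmer might require the onset date to be later than the dosing date. Then no routinely collected TEAE would belong to a Period 2 regimen, and an AE after the dose on Period 1 Day 1 would belong to no regimen. The SAP speaks of administration, not of dates, so this reading replaces the rule and defeats its purpose.

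**The case for a change.** The strongest case is that reproducibility should not rest on programmers' good sense when the written rule and the specified data do not match. The predose window is also not empty. Subjects are in the unit overnight, and a blood sample is drawn shortly before the dose. If the post-dose onset rate is r times the predose rate and h hours are observed after the dose, the predose share of that day's events is 8/(8 + r × h). With r = 1 and h = 10 this is 8/18 = 44%. With r = 5 and h = 16 it is 8/88 = 9%.

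It stands that neither document states that onset time is captured, or names a same-date convention. The rest is weaker:

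- The range of r has no source in the documents. A constant rate over hours largely spent asleep is doubtful, and h = 16 assumes check-out at midnight. A share of one day's events says nothing about how many there are.
- Protocol 10.2.1.2 lists what to document; it is not the form layout. Protocol 12.0 leaves data-handling detail to the Data Management Plan. The form may hold an onset time.
- Subjects are confined from Day -1 to check-out and dosed under observation with the time recorded. Staff already judge timing against dosing, both for the pretreatment/AE split and for causality (Protocol 10.1.6). The order can usually be recovered from source.
- SAP 7.1.4 concerns incomplete or missing dates, and here the date is complete. SAP 7.1.6 excludes imputation of missing data generally, but assigning by the recorded date fills in no value.

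**Conclusion.** This is a gap that analysts fill sensibly, and it calls for no change to the plan. The attribution rule is correct and readable. It can be applied with a recorded onset time or, failing that, with the ordinary same-day default. Under the default, the only possible error is a new event first noted in the roughly 8 hours before the Period 2 dose, at 1.9 percentage points per misplaced subject. No expected number can be given, because the documents state no adverse event rate.

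The conclusions do not depend on it. The objectives are bioequivalence and PK parameters (Protocol 5.1), safety is summarized without inferential testing (Protocol 13.1.4), and both regimens are esomeprazole 40 mg. Overall TEAE counts are the same under any same-day convention, because such events follow the first dose either way.

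This rests on two assumptions: that dosing stays close to 0800, and that programmers read the rule as order relative to the dose. The case report form was not available for this review. If it captures onset time, even the small window closes.

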7.4 Diet, Fluid, and Activity Control

7.4.1 Confinement

Subjects enrolled in this study will be confined in the clinical research unit for 1 night in each period, beginning at Check-in (Day -1) to the completion of all assessments on Day 1. There will be a minimum 6-day washout interval between the dose in the first period and the dose in the second period. Subjects will be released from the clinic during the washout interval.

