13.1.4 Safety Analysis

AEs will be summarized using the safety analysis set. No statistical testing or inferential statistics will be generated. All AEs will be coded using MedDRA. Data will be summarized using preferred term and primary system organ class.

For safety laboratory tests, vital signs, and ECG, data will be listed and summarized, as appropriate.

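### SAP 7.11.1: as written, the second adverse event attribution rule sends Period 1 and washout events to the Period 2 regimen; the word *last* appears to be missing

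*SAP*

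**What the plan says.** SAP 7.11.1 defines a treatment-emergent adverse event (TEAE) as one that "started or worsened after first study drug administration", with an outer limit of 30 days from the last dose. Two attribution rules follow.

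- **Rule 1.** A TEAE belongs to a regimen if it occurs "after administration of the study drug in a period and up to just prior to study drug administration in the next period".
- **Rule 2.** "A TEAE that occurs after administration of the study drug dose is attributed to the regimen received in the last period".

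The same section states that "TEAEs will be summarized by regimen and overall". It defines the most frequent TEAEs as those reaching at least 5% of a regimen's subjects, judged on the unrounded percentage.

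No other section supplies an attribution rule. Protocol 13.1.4 says only that adverse events are summarized on the safety set, and SAP 7.1.1 adds no study-specific definitions.

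**The concern.** Rule 1 closes each period at the next period's dose. Period 2 has no next period, so a second rule is needed for events after the final dose. Rule 2 is evidently meant to be that rule, but it does not say which dose it refers to. Every TEAE follows some dose, so rule 2 as worded excludes none of them.

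For a subject dosed in both periods, the two consecutive sentences give different answers for any event between the doses. This is the only rule that fills the regimen columns of the TEAE tables. Followed literally, all events in sequence AB would count for the tablet and all events in sequence BA for the capsule. Columns labelled by formulation would then hold a comparison of sequences.

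**Working it through.** The plan gives no figure to reproduce. The check compares the two rules case by case and then sizes the difference.

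**1. The rules side by side** (A = capsule, B = tablet; subjects dosed in both periods)

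| Sequence | Event time | Rule 1 | Rule 2 as written | Rule 2 with *last* inserted |
|---|---|---|---|---|
| AB | Period 1 | A | B | does not apply; rule 1 gives A |
| AB | Washout | A | B | does not apply; rule 1 gives A |
| AB | Period 2 | B (no end point) | B | B |
| BA | Period 1 | B | A | does not apply; rule 1 gives B |
| BA | Washout | B | A | does not apply; rule 1 gives B |
| BA | Period 2 | A (no end point) | A | A |

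As written, 4 of 6 cells conflict. With *last* inserted, none do. A subject dosed only in Period 1 has no conflict under either wording, because Period 1 is then also the last period.

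**2. Share of collection time in conflict**

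- Protocol 7.4.1: "There will be a minimum 6-day washout interval between the dose in the first period and the dose in the second period". The minimum is 6 × 24 = 144 h.
- Protocol 10.2.1.1: "Routine collection of AEs will continue until check-out following the completion of all assessments on Day 1 of Period 2". The last PK sample is at 10 h, so I take about 10 h after the second dose.
- Share: 144 / (144 + 10) = 93.5%. With 7 days between doses: 168 / (168 + 10) = 94.4%.

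This is clock time, not events. The documents give no event timing, so the share of events is an assumption. If events occur only in the 10 h after each dose at equal rates, it is 10 / (10 + 10) = 50%. If onset is uniform over time, it is about 94%.

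**3. Effect on the regimen columns**

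Take 26 subjects per sequence (Protocol Table 8.b), all completing. Assume per-period TEAE rates pA and pB that are the same in both periods.

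- Rule 1: capsule 26·pA + 26·pA = 52·pA; tablet 52·pB.
- Rule 2 as written: tablet receives all AB events, 26·(pA + pB); capsule receives all BA events, 26·(pB + pA).

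| Assumed pA, pB | Rule 1: capsule, tablet | Rule 2 as written: capsule, tablet |
|---|---|---|
| 5%, 15% | 2.6, 7.8 | 5.2, 5.2 |
| 10%, 20% | 5.2, 10.4 | 7.8, 7.8 |
| 10%, 30% | 5.2, 15.6 | 10.4, 10.4 |

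Under these assumptions the literal rule makes the expected counts equal whatever the true difference. If the rates differ by period, the literal tablet-minus-capsule difference is 26·[(pA1 − pB1) − (pA2 − pB2)]. If the formulation difference is larger in Period 1, which includes the washout, its sign would reverse.

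**4. The 5% cut**

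0.05 × 52 = 2.6 and 0.05 × 48 = 2.4, so the smallest qualifying count is 3 subjects at either size (3/52 = 5.8%, 2/52 = 3.8%; 3/48 = 6.3%, 2/48 = 4.2%). For example, suppose three AB subjects report the same washout event after the capsule, and no one else reports it. Rule 1 gives capsule 3/52 (5.8%) and tablet 0/52. Rule 2 as written gives capsule 0/52 and tablet 3/52, so the term enters the most-frequent table through the wrong column.

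**The case against.** The strongest reply is that nobody would program rule 2 literally. Rule 1 is specific and complete for Period 1 and the washout, and the literal rule 2 would leave it with no effect for anyone dosed twice. The reading that gives both sentences a purpose is that rule 1 runs to the next dose and rule 2 covers what follows the final one. Taking *the last period* to mean the period most recently dosed also removes the conflict. This has force: the intent is fairly evident. But the SAP states neither reading, and an operative rule should not depend on the programmer choosing the charitable one.

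The second reply is that little depends on it. Protocol 13.1.4 states: "No statistical testing or inferential statistics will be generated". TEAEs and dosing times are both listed (SAP 7.11.1 and 7.7), so a wrong assignment could be seen and corrected. The overall column is unaffected, and comparing adverse events is not a study objective. All of this stands and sets the grade.

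Third, the size figures are open to challenge. Uniform onset is a weak assumption for single doses of a drug with a half-life of about 1 hour (Protocol 6.2). The time share also depends on ending the count at check-out rather than at the SAP's 30-day limit. The three-subject example shows what is possible, not what is likely. These are fair limits on the size, but they do not remove the contradiction.

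**Conclusion.** The concern holds. As worded, rule 2 contradicts rule 1 for every event between the two doses in subjects dosed in both periods. The consequence is small. It reaches only the descriptive by-regimen TEAE tables and the 5% listing of frequent terms, and only if rule 2 is applied as written. The bioequivalence analysis in SAP 7.9.1 does not use event attribution.

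The logical conflict rests on the text alone. The affected share of events (about 50% to 94%) and the expected counts rest on the assumed timing and rates shown above. That a word was dropped is an inference, well supported because restoring it makes the two sentences complementary. This is a wording correction worth making, not a threat to the trial's conclusion.

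**What to change.** In the second attribution sentence of SAP 7.11.1, insert *last* before *study drug dose*, so that it applies only to events after the final dose. Rule 1 then governs Period 1 and the washout, rule 2 governs what follows, and a subject who stops after Period 1 is still handled correctly. Nothing else in the section needs to change. The cost is one word in the SAP, with no new data, visits, tables or analyses, and I see no downside.

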7.11.2 Clinical Laboratory Evaluations

Clinical safety laboratory tests include hematology, chemistry, urinalysis, and diagnostic screening. Refer to Appendix A for scheduled clinical laboratory test measurements and to Table 7.c for the list of all clinical laboratory tests.

Individual results for hematology and chemistry laboratory tests that meet the Takeda predefined laboratory markedly abnormal value (MAV) criteria in Appendix B will be presented in a data listing. If a subject has a MAV for a particular laboratory test, all visits for that subject for that parameter will be listed.

All clinical laboratory data will be presented in both SI and conventional units in the data listings. Laboratory data outside of the normal reference range will be listed. Out of normal range values and MAVs will be flagged in data listings.

Hematology	Serum Chemistry		Urinalysis
RBC WBC (with differential) Hemoglobin Hematocrit Platelets MCHC MCV RDW Reticulocyte count	Alanine aminotransferase Albumin Alkaline phosphatase Aspartate aminotransferas Glucose (a) Gamma-glutamyl transfer Total bilirubin Total protein Serum creatinine	ie ase	pH Specific gravity Protein Ketones Glucose Bilirubin Blood Nitrites Leukocyte esterase
PT/INR aPTT Diagnostic Screening:	Blood urea nitrogen Phosphorous Potassium Chloride Bicarbonate or carbon dioxide Sodium		Microscopic Analysis (only of positive dipstick result): RBC/high power field WBC/high power field Epithelial cells, casts
Serum		Urine	
HIV test Hepatitis panel, including HBsAg and anti-HCV Ab Female subjects: Human chorionic gonadotropin (for pregnancy) Female subjects of child-bearing potential only when menopause is suspected: Follicle-stimulating hormone		Drug screen, including alcoho barbiturates, benzodiazepines, opiates, and cotinine	l, amphetamines, cannabinoids, cocaine,

Table 7.c Clinical Laboratory Tests

anti-HCV Ab=anti-hepatitis C virus antibody, aPTT=activated partial thromboplastin time, MCH=mean corpuscular hemoglobin, MCHC=mean corpuscular hemoglobin concentration, MCV=mean corpuscular volume, PT=prothrombin time, RBC=red blood cell, RDW=red cell distribution width, WBC=white blood cell. (a) Conducted under fasting conditions.

